16.1.6.3. Hypersensitivity Reactions

Hypersensitivity reactions are those events recorded as MedDRA code in the pre-defined Standardized MedDRA Queries (SMQ) “Hypersensitivity” (narrow).

Hypersensitivity reaction adverse events of special interest (Hypersensitivity reactions AESI) are those events both identified as Hypersensitivity reaction adverse events and recorded as “Adverse Event of Special Interest” equal to “Yes” on the Adverse Events page of the eCRF.

Hypersensitivity reactions will also be listed. The listing will include the “Adverse Event of Special Interest” equal

Document: \\ieedc-nas01a:\Boehringer_Ingelheim\BI_695501\XXA39605\Biostatistics\Documentation\SAP\15-v2.0\BI 1297.12 SAP v2.0 31JAN2018.docx

Author: Version Number: 2.0
Version Date: 31JAN2018

Template No: CS_TP_BS016 Revision 4
Effective Date: 01Apr2016

Reference: CS_WI_BS005

to “Yes” information from the Adverse Events page of the eCRF as a flag.

16.1.6.4. Drug Induced Liver Injury (DILI)

Drug Induced Liver Injury (DILI) are those events identified by medical advisor on the subset of AEs for subjects presenting laboratory potential DILI findings (refer to section 16.3.1)

DILI events of special interest (DILI AESI) are those events both identified as DILI adverse events and recorded as “Adverse Event of Special Interest” equal to “Yes” on the Adverse Events page of the eCRF.

Drug Induced Liver Injury (DILI) will be listed. The listing will include the “Adverse Event of Special Interest” equal to “Yes” information from the Adverse Events page of the eCRF as a flag.

16.1.6.5. Injection-site reactions

Injection-site reactions are those events recorded with MedDRA high level terms (as listed in BlcMQs Administration site reaction subsearches 1,2,4 and 5, with a version consistent with the MedDRA version, refer to APPENDIX 4):

- Administration site reactions NEC
- Application and instillation site reactions
- Infusion site reactions
- Injection site reactions

Moreover, the number and percentage of subjects with injection site reactions will be summarized for each injection site reaction (Swelling / Hardening / Heat / Redness / Pain / Itching / Bruising / Other).

Injection-site reactions will be listed.

16.1.6.6. Anaphylactic reactions

Anaphylactic reactions are those events recorded as MedDRA code in the pre-defined Standardized MedDRA Queries (SMQ) = “Anaphylactic reactions” (narrow)

Anaphylactic reaction adverse events of special interest (Anaphylactic reaction AESI) are those events both identified as Anaphylactic reactions and recorded as “Adverse Event of Special Interest” equal to “Yes” on the Adverse Events page of the eCRF.

Anaphylactic reactions will also be listed. The listing will include the “Adverse Event of Special Interest” equal to “Yes” information from the Adverse Events page of the eCRF as a flag.

Document: \\eedc-nas01a:\Boehringer_Ingelheim\BI_695501\XXA39605\Biostatistics\Documentation\SAP\15
-v2.0\BI 1297.12 SAP v2.0 31JAN2018.docx

Author: Version Number: 2.0
Version Date: 31JAN2018

Template No: CS_TP_BS016 Revision 4
Effective Date: 01Apr2016

Reference: CS_WI_BS005

16.1.7. AES OCCURRING AFTER THE LAST INJECTION FOR SUBJECTS DISCONTINUED DUE TO LACK OF EFFICACY

Subjects who discontinued treatment due to lack of efficacy will be identified from “End of treatment visit” eCRF page, where “Reason for End of Treatment” is “Lack of Efficacy”.

Number of subjects, percentages, and number of events occurring after the last injection and prior to the last injection + 10 weeks for subjects discontinued due to lack of efficacy by SOC and PT will be prepared.

AEs occurring after the last injection and prior to the last injection + 10 weeks for subjects discontinued due to lack of efficacy will be listed.

16.2. DEATHS

If any subjects die during the trial as recorded on the “End of Treatment” page or the “Trial Completion” page or the “Safety Follow-Up” page or the AE page (SAE which “Results in death” or AE with “Fatal” outcome) or the “Death” form, the information will be presented in a summary table and a data listing.

16.3. LABORATORY EVALUATIONS

Results from the central laboratory will be included in the reporting of this trial for Serum Chemistry, Hematology and Urinalysis. A list of laboratory assessments to be included in the outputs is included in APPENDIX 5.

Presentations will use SI and US Units.

Quantitative laboratory measurements reported as “< X”, i.e., below the lower limit of quantification (BLQ), or “> X”, i.e., above the upper limit of quantification (ULQ), will be converted to X for the purpose of quantitative summaries, but will be presented as recorded, i.e., as “< X” or “> X” in the listings.

Qualitative laboratory urinalysis results measured by central laboratory will be classified to the categories “Positive” and “Negative” based on the central laboratory normal reference.

The handling of retests, unscheduled, and end of trial measurements is described in Section 6.3. However, laboratory values taken after the first dose of trial medication up to the end of a period (i.e. up to 10 weeks after the last dose of the trial medication) will be assigned to the treatment phase for evaluation. Moreover, tables about DILI will include unscheduled visits.

All available data will be listed.

The following summaries will be provided for laboratory data:

- Actual and change from baseline by visit (for quantitative measurements)
- Shifts from baseline category (Low/ Normal/ High) by visit (except for urinalysis)

Document: \\eedc-nas01a:\Boehringer_Ingelheim\BI_695501\XXA39605\Biostatistics\Documentation\SAP\15-v2.0\BI 1297.12 SAP v2.0 31JAN2018.docx

Author: Version Number: 2.0
Version Date: 31JAN2018

Template No: CS_TP_BS016 Revision 4
Effective Date: 01Apr2016

Reference: CS_WI_BS005

- Shift from baseline category (Negative/ Positive) by visit (for urinalysis)
- Listing of subjects meeting abnormal criteria
- Proportion of possible Hy's law subjects
- Proportion of possible Drug Induced Liver Injuries (DILIs)
- The time course of ALT, AST and total bilirubin (TBL) for all possible Hy's law subjects, all parameters shown on a logarithm to base 10 scale of the multiple of the upper limit of normal (ULN) (Y axis) versus days since treatment start (X axis).
- Scatter plots for Evaluation of Potentially Drug-Induced Liver Injury:
 - log ALT on the X axis and log TBL on the Y axis, both shown on a logarithm to base 10 scale of the multiple of the ULN
 - log AST on the X axis and log TBL on the Y axis, both shown on a logarithm to base 10 scale of the multiple of the ULN.

Baseline is described in section 6.2.

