FLOW CHART

Visit ¹	1	2	3	4	5	6	7	8	9	10												
Week	Screen -4 to -1	Base line 0	1	3	4	5	7	8	9	11	12	13	15	16	17	19	20	21	23	24 EoT	33 SFU ²	
Days	-28 to -1 ¹¹	1	8	22	29	36	50	57	64	78	85	92	106	113	120	134	141	148	162	169	232	
Permitted visit window (days)	-	-1/ +2	± 2	± 2	± 2	± 2	± 2	± 2	± 2	± 2	± 2	± 2	± 2	± 3	± 3	± 3	± 3	± 3	± 3	± 3	± 3	+ 3
Informed consent	X																					
Assessment of eligibility	X	X																				
Demographics	X																					
Medical history	X																					
LAB/SAFETY ASSESSMENTS³																						
Infection screen: TB, hepatitis B (HBsAg, anti- HBc), hepatitis C (anti-HCV), HIV	X																					
Chest X-ray	X ⁴																					
TB testing (IGRA or PPD testing) ⁵	X																					X
Pregnancy test	X	X						X						X							X	X
Physical examination	X	X						X						X							X	X
Vital signs ⁶	X	X						X						X							X	X
Safety Laboratory tests	X	X						X						X							X	X
12-lead ECG	X							X						X							X	X

Visit ¹	1	2	3	4	5	6	7	8	9	10	11	12	13	14	15	16	17	18	19	20	21	22	23	24	25	26	27	28	29	30	31	32	33		
Week	Screen -4 to -1	Base line 0	1	3	4	5	7	8	9	11	12	13	15	16	17	19	20	21	23	24 EoT	33 SFU ²														
Days	-28 to -1 ¹¹	1	8	22	29	36	50	57	64	78	85	92	106	113	120	134	141	148	162	169	232														
Permitted visit window (days)	-	-1/ +2	± 2	± 2	± 2	± 2	± 2	± 2	± 2	± 2	± 2	± 2	± 2	± 3	± 3	± 3	± 3	± 3	± 3	± 3	± 3	± 3	± 3	± 3	± 3	± 3	± 3	± 3	± 3	± 3	± 3	± 3			
Previous and concomitant therapy	←-----X-----→																																		
Adverse events ⁷	←-----X-----→																																		
EFFICACY ASSESSMENTS³																																			
PASI	X	X			X			X			X			X			X			X															
sPGA	X	X			X			X			X			X			X			X															
DLQI	X	X			X			X			X			X			X			X															
TRIAL MEDICATION																																			
Contact IRT ¹¹	X	X	X ₁₂		X ₁₂			X ₁₂			X ₁₂			X ₁₂			X ₁₂			X ₁₂															
Trial medication ⁹		X	X	X		X	X		X	X		X	X		X	X		X	X		X	X													
Review patient diary ¹³					X ¹³			X ¹³			X ¹³			X ¹³			X ¹³			X ¹³								X ¹³	X ¹³						
Randomization ¹⁰		X																																	

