5.3.3 Safety laboratory parameters

The laboratory tests listed in [Table 5.3.3: 1](#) will be analyzed by a central laboratory. The central laboratory provider will also provide the materials for blood sampling. Instructions for the labeling, storage, and shipment of the samples as well as details of all blood variable units and reference ranges can be found in the Laboratory Manual.

Pregnancy testing will be performed by a central laboratory using serum at Screening and local laboratory using urine at all applicable visits thereafter.

For time points of laboratory sampling, see the [Flow Chart](#).

Laboratory results (i.e., all safety laboratory and clinical laboratory data relevant for current clinical practice) of the patients will be available to the respective investigator (via laboratory reports) and to the sponsor (via the central laboratory website) and selected abnormal laboratory alerts will be flagged to the site and sent to sponsor in real time.

The investigator must assess all laboratory results, evaluate any change in laboratory values, and review all clinical laboratory tests for potential clinical significance at all time points throughout the trial. The investigator should endeavor to provide a reason for all out-of-range results deemed not clinically significant. If the investigator determines a laboratory abnormality to be clinically significant, it will be considered an AE / SAE (see Section 5.3.6.1); however, if the laboratory value abnormality is consistent with a current diagnosis, it will be documented accordingly.

Table 5.3.3: 1 Laboratory tests

Category	Test name
Haematology	Hct Hb RBC count / erythrocytes White blood cells / leukocytes Platelet count / thrombocytes
Diff. Automatic	Neutrophils (relative count) Lymphocytes (relative count)
Diff. Manual (if Diff Automatic is abnormal)	Neutrophils, bands (stabs) Neutrophils, polymorphonuclear Lymphocytes
Enzymes	AST (GOT) ALT (GPT) Creatine Kinase CK-MB, only if CK is elevated Gamma-Glutamyl Transferase (GGT)
Electrolytes	Calcium Sodium Potassium Chloride
Substrates	Glucose Creatinine Bilirubin total Bilirubin direct (if total is elevated) Bilirubin indirect (if total is elevated) Total protein Albumin Cholesterol, total
Urine Pregnancy test (only for female patients of childbearing potential) at randomization and continued as indicated in the Flow Chart (including EoT and End of Observational Period Visit)	Human Chorionic Gonadotropin in the urine

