6. INVESTIGATIONAL PLAN

6.1 VISIT SCHEDULE

A schedule of assessments is provided in the [Flow Chart](#).

Each visit date (with its window) is to be counted from Day 1 (randomization). If any visit has to be rescheduled, the 2-week regimen for trial medication administration should resume from the time the last dose was administered. Additional visits for the purpose of re-testing of laboratory parameters or AE monitoring may be included as deemed necessary by the investigator.

- A visit window of -1 / + 2 days is permitted for Visit 2 (Day 1)
- A visit window of ± 2 days is permitted from Visit 3 up to Visit 7
- A visit window of ± 3 days is permitted for Visit 8 to Visit 10

All assessments should be performed prior to administration trial medication, unless otherwise specified. Laboratory samples must be drawn prior to trial medication injection.

The questionnaire will be completed at the site by the patient (DLQI) before any investigations or discussions about their disease with the clinic staff and may only be recorded by a trial nurse/investigator on behalf of the patient if the patient has difficulty writing during the visit or is unable to read. This must be documented clearly in the patient notes.

Also the scales are to be completed by study site personnel (PASI sPGA,

All questionnaires and scales are detailed in Appendix 10.

The total estimated volume of blood that will be drawn from each patient during the course of the trial is shown in [Table 6.1: 1](#).

Table 6.1: 1 Estimated blood sample volumes per patient

Parameter	Sample volume (mL)	Number of samples	Total volume (mL)
Laboratory tests (including serum chemistry, serum pregnancy test)	3	6	18
Hematology	3	6	18
Infection screen	4	1	4
TB test	3	2	6
Approximate total			82

Abbreviations: ADA=anti-drug antibodies; nAb=neutralizing ADA; TB=tuberculosis.

Additional samples may be required if medically indicated, e.g., at unscheduled visits to follow safety findings.

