7.3.4 Safety analyses

Adverse events will be coded using the Medical Dictionary for Drug Regulatory Activities (MedDRA). The analysis of AEs will be based on the concept of treatment-emergent AEs. That means that all AEs with an onset between start of treatment and end of the REP, a period of 10 weeks after the last dose of trial medication, will be assigned to the treatment

period for evaluation. AEs that start before first drug intake and deteriorate under treatment will also be considered as ‘treatment-emergent’. Other AEs will be assigned to the appropriate trial phases, i.e., screening or post-treatment.

All treated patients will be included in the safety analysis. In general, safety analyses will be descriptive in nature and will be based on BI standards. No hypothesis testing is planned.

Statistical analysis and reporting of adverse events will concentrate on treatment-emergent adverse events. To this end, all adverse events occurring between start of treatment and end of the residual effect period will be considered ‘treatment-emergent’. The residual effect period is defined as 10 weeks after last dose of trial medication. Adverse events that start before first drug intake and deteriorate under treatment will also be considered as ‘treatment-emergent’.

Frequency, severity, and causal relationship of adverse events will be tabulated by system organ class and preferred term after coding according to the current version of the Medical Dictionary for Drug Regulatory Activities (MedDRA).

Laboratory data will be analysed both quantitatively as well as qualitatively. The latter will be done via comparison of laboratory data to their reference ranges. Values outside the reference range as well as values defined as clinically relevant will be highlighted in the listings. Treatment groups will be compared descriptively with regard to distribution parameters as well as with regard to frequency and percentage of patients with abnormal values or clinically relevant abnormal values.

Vital signs, physical examinations, or other safety-relevant data observed at screening, baseline, during the course of the trial and at the end-of-trial evaluation will be assessed with regard to possible changes compared to findings before start of treatment.

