APPENDIX 5. LABORATORY ASSESSMENTS

Laboratory parameter	SI unit	US unit
Serum chemistry		
Creatinine	umol/L	mg/dL
Alkaline phosphatase	IU/L	IU/L
Aspartate aminotransferase (AST)	IU/L	IU/L
Alanine aminotransferase (ALT)	IU/L	IU/L
Gamma glutamyl transpeptidase (GGT)	IU/L	IU/L
Total bilirubin	umol/L	mg/dL
Direct bilirubin	umol/L	mg/dL
Glucose	mmol/L	mg/dL
Total cholesterol	mmol/L	mg/dL
Total protein	g/L	g/dL
Sodium	mmol/L	mEq/L
Potassium	mmol/L	mEq/L
Chloride	mmol/L	mEq/L
Calcium	mmol/L	mg/dL
Albumin	g/L	g/dL
Hematology		
Hemoglobin	g/L	g/dL
Hematocrit	V/V	%
Erythrocyte	10 ¹² /L	10 ⁶ /uL
Platelets	10 ⁹ /L	10 ³ /uL
White blood cells	10 ⁹ /L	10 ³ /uL
Lymphocytes	10 ⁹ /L	10 ³ /uL
Neutrophils	10 ⁹ /L	10 ³ /uL
Urinalysis		
Protein	g/L	g/dL
Glucose	mmol/L	mg/dL
Blood	N/A	N/A

Document: \\ieedc-nas01a:\Boehringer_Ingelheim\BI_695501\XXA39605\Biostatistics\Documentation\SAP\15
-v2.0\BI 1297.12 SAP v2.0 31JAN2018.docx

Author: Version Number: 2.0
Version Date: 31JAN2018

Template No: CS_TP_BS016 Revision 4
Effective Date: 01Apr2016

Reference: CS_WI_BS005

Copyright © 2009, 2010, 2012, 2016

All rights reserved.

The contents of this document are confidential and proprietary to
reproduction is strictly prohibited.

Unauthorized use, disclosure or

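### SAP Appendix 5 leaves creatine kinase, a scheduled protocol laboratory test, out of the between-arm tables and lists alkaline phosphatase, which the protocol names only in the triggered liver work-up

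*SAP*

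**What the plan says.** Protocol 5.3.3 states that the tests in Table 5.3.3: 1 "will be analyzed by a central laboratory". The enzyme rows of that table are AST, ALT, creatine kinase, reflex CK-MB and GGT. The extracted text runs two of these rows together as "Creatine Kinase CK-MB, only if CK is elevated". Alkaline phosphatase is not in the table.

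The Flow Chart row "Safety Laboratory tests" schedules the panel at Screening, Baseline, Weeks 8, 16 and 24, and safety follow-up. Protocol Table 6.1: 1 agrees, giving 6 samples for "Laboratory tests (including serum chemistry, serum pregnancy test").

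For the analysis, protocol 7.3.4 says "Treatment groups will be compared descriptively with regard to distribution parameters", and also by the frequency of abnormal values. No analyte is excepted.

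SAP 16.3 plans by-visit actual values and changes from baseline, and low/normal/high shifts. It defines the parameters by reference: "A list of laboratory assessments to be included in the outputs is included in APPENDIX 5". Appendix 5 has 15 serum chemistry rows. "Alkaline phosphatase" is one of them; creatine kinase and CK-MB are not.

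**The concern.** Comparing the safety profiles of the two products is a stated secondary objective (protocol 2.2, SAP 2.2). The plan takes creatine kinase from every patient on a fixed schedule and then provides no table in which its distribution or its shift to abnormal can be compared between arms. A programmer working from Appendix 5 would leave it out without departing from the SAP. The same programmer would build by-visit tables for alkaline phosphatase, and the protocol does not say where scheduled values of it would come from.

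The SAP says it is based on protocol version 1.0, the version at hand, so a later protocol does not explain the difference. The available SAP text gives no reason for it.

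**Working it through.** The plan states no figure to reproduce. The check is an item-by-item comparison of the two lists, followed by a simple count.

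**Serum chemistry.** Scheduled (non-reflex) analytes in Table 5.3.3: 1:
- enzymes: AST, ALT, creatine kinase, GGT = 4
- electrolytes: calcium, sodium, potassium, chloride = 4
- substrates: glucose, creatinine, total bilirubin, total protein, albumin, total cholesterol = 6

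Total: 4 + 4 + 6 = 14. Of these, 13 are in Appendix 5. The missing one is creatine kinase.

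The 15 rows of Appendix 5 break down as those 13, plus direct bilirubin (a reflex test in the protocol), plus alkaline phosphatase: 13 + 1 + 1 = 15.

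| Item | Protocol Table 5.3.3: 1 | SAP Appendix 5 |
|---|---|---|
| Creatine kinase | Scheduled | Absent |
| CK-MB | Reflex, if CK is elevated | Absent |
| Indirect bilirubin | Reflex | Absent |
| Manual differential | Reflex | Absent |
| Direct bilirubin | Reflex | Present |
| Alkaline phosphatase | Absent | Present |
| Neutrophils, lymphocytes | Relative count | 10^9/L (absolute) |

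The remaining hematology and urinalysis items match.

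**Is creatine kinase itself scheduled, or only reflex?** The condition applies to CK-MB. It presupposes that creatine kinase has already been measured, so creatine kinase is a routine test.

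**Does Appendix 5 control the tables?** SAP 16.3 says so. SAP 6.3 also ties its rule for using retests in by-visit summaries to the assessments in Appendix 5.

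**Where does the protocol call for alkaline phosphatase?** Only in Appendix 10.1.2, after a confirmed liver alert. SAP 6.3 keeps unscheduled values out of by-visit summaries unless they are assigned to a planned visit, with an exception for DILI. On the protocol's terms, alkaline phosphatase would therefore not normally reach a by-visit table.

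**Size.** Scheduled samples: 6 per patient. Pre-treatment: 2 (Screening, Baseline). Post-baseline: 6 − 2 = 4 (Weeks 8, 16 and 24, follow-up). With about 300 patients, 4 × 300 = 1,200 post-baseline creatine kinase results at most. Missed visits and discontinuations reduce this.

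**The case against.** The best case against the point has four parts.

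**The actual panel is not shown.** Protocol 5.3.3 refers units and reference ranges to a Laboratory Manual that is not among these documents. The SAP is dated 31 January 2018, and its section 15.1.2.2 says the burn-in was set on roughly 90% of subject data up to Week 16, so its authors had most of the data. An alkaline phosphatase row with SI and US units is quite compatible with the laboratory having run it. This stands. A reader might infer that the alkaline phosphatase tables will be empty, but the documents show only that the protocol schedules none.

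**Creatine kinase is not lost altogether.** SAP 16.3 lists all available data. Under protocol 5.3.3 a clinically significant abnormality becomes an adverse event unless it fits a current diagnosis, and SAP 16.1.2 tabulates adverse events. This also stands. It would be too strong to say that creatine kinase is never compared between arms. But a listing is not a comparison, and adverse events capture what investigators judged significant, not a shift in distribution. Neither supplies what protocol 7.3.4 promises.

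**The count can be overstated.** All six samples give 6 × 300 = 1,800, but the two pre-treatment samples hold no on-treatment comparison. The figure of 1,200 excludes them, and either count measures data volume, not effect on a conclusion.

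**Creatine kinase is peripheral.** It is not an endpoint, not an adverse event of special interest, and not part of the hepatic injury or Hy's law definitions. ALT, AST and bilirubin, which are, all appear in Appendix 5. This limits the importance of the point but does not remove the mismatch.

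**Conclusion.** The two lists disagree in both directions, and the creatine kinase omission is an error as written. The protocol schedules the test at six visits and commits to a descriptive comparison of laboratory data by arm; the SAP's controlling list drops it. Up to about 1,200 post-baseline results would have no by-visit, change-from-baseline or shift table. This assumes that the laboratory ran the panel in Table 5.3.3: 1.

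For alkaline phosphatase the supportable conclusion is narrower: its presence in Appendix 5 is unexplained and has to be reconciled with the panel. Which list matches the data cannot be settled from the documents.

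The neutrophil and lymphocyte difference is a discrepancy in how the counts are expressed. Neither document says how the absolute values arise, so no derivation should be assumed.

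Overall the issue is minor. Safety analyses are descriptive with no hypothesis testing, and the primary equivalence conclusion is unaffected.

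**What to change.** - Add creatine kinase to SAP Appendix 5 and to the by-visit, change-from-baseline and shift tables. List CK-MB only: as a reflex test it covers a selected subset, mostly without baseline values, so shift tables would say little.
- Check alkaline phosphatase against the actual central-laboratory panel. If it comes only from the liver work-up, take it out of the by-visit outputs. If it was added to the panel, document that and bring Table 5.3.3: 1 and Appendix 5 into line.
- Confirm with the laboratory whether neutrophils and lymphocytes are reported as relative or absolute counts, and use the same form in both lists.

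The cost is a few rows in an appendix, one more parameter in existing table programs and one query to the laboratory. No new data are needed if the scheduled panel was run.
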